Our proposed study seeks to shift the paradigm for promoting diet intake and physical activity using education and self-report to provide a powerful combination of mHealth dietary app and health coaching (set goals, provide ongoing feedback, and self-monitor behaviors). To our knowledge, this is the first time a mHealth dietary app and health coaching intervention has been used in kidney transplant recipients to link real-time data for monitoring dietary intake and physical activity.

The long-term goal of this work is to enhance well-being in kidney recipients via lifestyle self-management of care for dietary intake and physical activity to ultimately prevent chronic diseases. The proposed study is important because early weight gain after kidney transplant is associated with adverse effects on the transplanted kidney function resulting in increased health care cost and poor quality of life.⁷ Interventions are needed to monitor kidney transplant recipients diet and physical activity in real-time to prevent health decline.

The goal of the proposed feasibility study is to recruit a sample (N = 20) of post-kidney transplant recipients (age 18 and above) who will receive the mHealth dietary app + health coaching intervention for 12 weeks. We will assess changes over time for the primary outcome and secondary outcomes from baseline to 4, 8, and 12 weeks. We plan to submit our findings for publication to the Journal of Progress of Transplantation (Impact factor 0.958) or Trends in Transplantation (Impact factor 0.1.69). We *hypothesize* that the mHealth dietary app + health coaching intervention will improve adherence for recording diet and physical activity, decrease perceived stress, increase exercise self-efficacy, increase vegetable intake, decrease fat intake, decrease carbohydrate intake, improve weight control, improve blood pressure control, improve heart rate and an increase the number of minutes of physical activity per day. We will

also examine biological differences among the secondary outcomes of perceived stress, exercise self-efficacy, vegetable intake, fat intake, carbohydrate intake, weight, blood pressure, heart rate and minutes of physical activity per day, as previous studies have reported differences in outcomes based on age, sex, and race.^{8,9} The rationale for our hypothesis is that progression of cardiovascular disease and chronic disease may be slowed with daily tracking of dietary and physical activity.

II. Procedures

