Participant **Demographic Information** (10 minutes) will be obtained using a seven-item questionnaire demographics form and **Comorbidity Data** will be gathered using the Charlson Comorbidity Index³³ to describe the patient population. **Aim 1: Recruitment** (percent approached),

will be recorded in REDCap by the RA. **Retention** (percent dropped) will be recorded in REDCap by the RA. **Adherence** (percent to adhere to logging daily dietary intake and physical activity) will be recorded continuously each day by the “Lose-It” app. **Aim 2: Perceived Stress** (10 minutes) will be evaluated by using the Perceived Stress Scale (PSS).³⁵ The PSS is a 10-item questionnaire using a Likert Scale to rate feelings of stress from 0 “never” to 4 “very often.” The PSS has demonstrated excellent test-retest reliability (intraclass correlation coefficient = 0.954) and internal consistency (Cronbach's alpha = 0.810) with adults who have chronic disease.³⁶ **Exercise Self-Efficacy** (10 minutes) will be evaluated by using the Self-Efficacy for Exercise (SEE) Scale. The SEE is a 9-item questionnaire using a Likert Scale to rate feelings of stress from 0 “not confident” to 10 “very confident.” The SEE has demonstrated excellent internal consistency ($\alpha = 0.92$) for adults living with chronic disease.³⁷ **Vegetable intake** will be measured using the Block Fruit-Vegetable-Fiber Screener. The Block Fruit-Vegetable-Fiber Screener (5 minutes) has demonstrated high reliability (Spearman r -value of 0.71).³⁸ This brief screening tool includes seven questions about fruit and vegetable intake and three questions about foods high in fiber, magnesium, and potassium. **Fat Intake and Carbohydrate Intake** (5 minutes) will be recorded each day by the participant using the “Lose-It” app. **Weight** will be measured each day by the participant using a wireless Wi Fi weight scale. The data from the wireless weight scale will sync the data from the participant's mobile phone to the premium password-protect “Lose-It” database each day. **Blood Pressure and Heart Rate** will be recorded each day by the participant using a wireless Wi Fi blood pressure cuff. The data from the wireless cuff will sync from the participant's mobile phone to the premium password-protect “Lose-It” database each day. **Minutes of Physical Activity per Day** will be recorded each day by the participant using the “Lose-It” app. **Clinical Frailty Scale** (5 minutes) will be used to measure the frailty level of each participant. The screening tool has demonstrated high reliability in adults. This brief screening tool consist of nine questions about a person's level of frailty.

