
D. Detailed study procedures

The “Lose-It” app will be set up with Gmail accounts with unique unidentifiable codes developed by the research team. Participants will be instructed how to download the “Lose-It” app virtually using Zoom. In addition, participants will be taught how to sync to their smartphone and retrieve data from their app. The participants will be trained to enter their dietary intake and physical activity daily for 12-weeks.

Participants will monitor their vegetable intake, fat intake, carbohydrate intake, weight, blood pressure, heart rate and the minutes of physical activity per day using the “Lose-It” app. Wi-Fi connected weight scales and blood pressure cuff will be supplied for weight and blood pressure monitoring. Participants will be taught how to sync the data from the scales and blood pressure cuff to the “Lose-It” app using the Premium database which will Sync all of the data into password protected database for the research team to access. Participants will perform a return demonstration to confirm that they can record their dietary intake daily, physical activity, weight, and blood pressure using the “Lose-It” app. We also review with the participant the “My Plate” method for proper nutrition and the steps to distance conversion chart. Each participant will be given a copy of both via email.

Session	mHealth App + Health Coaching Intervention Setting: Online video- conference call (Zoom)
Baseline Session (Session 1)	The research assistant (RA) will demonstrate proper “Lose-It” app use, set up the smartphone application, and how to enter their dietary intake, physical activity, weight, blood pressure, heart rate and the minutes of physical activity per day using the “Lose-It” app. The RA will demonstrate how to sync the data from the Wi Fi weight scales and blood pressure cuff to the “Lose-It” app.
Time for session: 90 minutes	Participants will perform a return demonstration to confirm that they can access the “Lose-It” app, sync the data from the Wi Fi scales and blood pressure cuff.

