Descriptive statistics will be used to summarize sample characteristics. **Aim 1)** percent approached, percent dropped, and percent to adhere to logging daily dietary and physical activity will be analyzed using means and standard deviations of these variables and analyzed as differences between the baseline and 3-month measurements using the Wilcoxon Signed-Ranked test. **Aim 2)** Perceived Stress Scale, Exercise Self-efficacy Scale, Fruit, Vegetables, and Fiber Screener, fat intake, carbohydrate intake, weight, blood pressure, heart rate, and the minutes of physical activity per day will be analyzed using the differences among baseline, 4, 8, and 12 weeks using repeated measures analysis of variance using the Friedman's Test. Frailty levels will be collected at baseline and 12 weeks and will be analyzed using means and standard deviations of this variables. **Missing Data:** We will carefully record and code various reasons for missing data (e.g., participants forgot to record data into the "Lose-It" app) and examine the pattern of missing data.

III. Bibliography

2. Aksoy N. Weight Gain After Kidney Transplant. *Exp Clin Transplant.* 2016;14(Suppl 3):138-140.

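### Daily home weight, blood pressure and heart rate have no set reading conditions and no rule reducing them to the four compared values; if the training-call reading became the baseline for blood pressure or heart rate, a first-use effect could pass for improvement.

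*Combined protocol and SAP*

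**What the plan says.** Section I sets the design: the study will "recruit a sample (N = 20) of post-kidney transplant recipients" "who will receive the mHealth dietary app + health coaching intervention for 12 weeks". There is no comparison group. The hypothesis in the same section is that the intervention will, among other things, "improve weight control, improve blood pressure control, improve heart rate".

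Section II.C has the participant take the readings. Weight "will be measured each day by the participant using a wireless Wi Fi weight scale"; blood pressure and heart rate "will be recorded each day by the participant using a wireless Wi Fi blood pressure cuff". Apart from the device and the daily frequency, nothing is fixed: no time of day, rest, posture, clothing or number of readings per occasion.

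Section II.D says that "Wi-Fi connected weight scales and blood pressure cuff will be supplied for weight and blood pressure monitoring". It describes no run-in and no device reading before training. On training it says: "Participants will perform a return demonstration to confirm that they can record their dietary intake daily, physical activity, weight, and blood pressure". The session table puts a return demonstration in Session 1, the 90-minute video call labelled as the baseline session, and words it as confirming that participants can open the app and sync the scale and cuff.

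Section II.F says that the secondary outcomes, including these three, "will be analyzed using the differences among baseline, 4, 8, and 12 weeks", by Friedman's test. It does not say which reading, or which average of readings, stands for each time point.

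**The concern.** Friedman's test needs one value per person per time point. Twelve weeks of daily recording give about 12 × 7 = 84 readings per person for each measure. Someone must reduce these to four, and the plan leaves that choice open until the data are in hand. Conditions that varied when the readings were taken cannot be standardised at the analysis stage.

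For blood pressure and heart rate there is a further risk. The first study-device reading that the plan describes comes from a supervised training call by a first-time user; later readings are unsupervised and taken by a practised user. If the training reading runs high and is used as baseline, the excess appears as a fall at every later time point, in the direction of the hypothesis. With one arm, no parallel series can reveal or remove it.

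For weight, a watched first reading has no evident effect on a scale. The issue there is time of day and clothing, which add noise of no known direction.

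At stake are the before-after estimates for three secondary outcomes, and any effect size or SD carried into the larger multisite trial that section II.E has in view.

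**Working it through.** The plan states no SD, significance level, power or effect size, so it offers no figure to reproduce. What follows is conditional illustration, using systolic blood pressure.

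**Inputs from the documents:** n = 20, one arm; four time points; Friedman's test.

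**Assumed inputs:** within-person day-to-day systolic SD 10 mmHg (range 8 to 12); two-sided 5% level; no true change; a first-reading offset of 3, 5 or 8 mmHg at baseline only; one reading per time point.

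**Step 1. Effect of an offset on the estimate.** Mean change = later mean − baseline mean. With no true change and a baseline high by *d*, this is −*d*: the whole offset becomes an apparent fall of 3, 5 or 8 mmHg.

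**Step 2. Effect on the test.** Share of 20,000 simulated trials per setting in which Friedman's test (chi-square, 3 df) is significant at 0.05:

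| Daily SD (mmHg) | Offset 0 | 3 | 5 | 8 |
|---|---|---|---|---|
| 8 | 5% | 16% | 37% | 79% |
| 10 | 5% | 11% | 24% | 57% |
| 12 | 5% | 9% | 18% | 42% |

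Repeat runs agree to within about one percentage point. For scale, the paired change detectable with 80% power from single readings at SD 10 is about (1.96 + 0.84) × 3.16 = 8.9 mmHg, so the largest offset shown is close to the smallest effect the study could reliably detect.

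**Step 3. Precision.** Standard error of mean change = √(V × 2/20), where V is the within-person variance of one time-point value.

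| Value used at both ends | V | SE | SE with week-to-week SD 4 (V + 16) |
|---|---|---|---|
| Single reading | 100 | 3.16 | 3.41 |
| 7-day mean, independent days | 100/7 = 14.3 | 1.20 | 1.74 |
| 7-day mean, lag-1 correlation 0.3 | 100 × 0.240 = 24.0 | 1.55 | 2.00 |

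The factor 0.240 is (1/7)[1 + 2Σ(1 − k/7)0.3^k] for k = 1 to 6.

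**Step 4. What averaging does to the offset.** These runs assume daily SD 8 and window-to-window SD 2. If an 8 mmHg offset affects only the first reading, a 7-day baseline mean that includes it gives an 11% false-positive rate; leaving it out returns the rate to 5%. If the offset halves each day, leaving out the first reading still gives 13%.

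**Step 5. Where averaging can hurt.** If a 2 mmHg novelty effect lasted through the whole baseline week, the more precise 7-day means would detect it in about 17% to 27% of trials (SD 10, no week-to-week variation), against 7% with single readings.

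**The case against.** A reader might infer that the plan uses the training-call reading as baseline and one reading at each later visit, so that the bias is built in. The documents do not support that. Section II.F says only baseline, and section II.C says only daily; a later reading on the same day or a first-week mean would fit the text equally well. Section II.D does not say that the demonstration yields a reading for analysis, and the Session 1 row speaks of access and syncing. This objection stands in full: what is documented is that the time-point value is undefined, not that a poor one was chosen.

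The offset is also assumed. No document supports 3 to 8 mmHg, and the simulation shows only what follows if a shift exists. A further tempting reading, that weight is exposed to the same first-use effect, fails because no mechanism for it is evident.

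Finally, these are secondary outcomes of a 20-person feasibility study. Without a control arm, change from baseline could not be attributed to the intervention even with perfect readings. That limits the consequence. It does not answer the missing conditions and missing summary rule, which nothing else in the document supplies.

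**Conclusion.** The gap is real and should be closed, though it does not threaten the study's main purpose. Two parts rest on the text alone: no reading conditions are set for any of the three measures, and no rule turns daily readings into the compared values. The first-reading mechanism is a possibility confined to blood pressure and heart rate, because the plan does not name the baseline reading.

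The false-positive rates hold only if the demonstration reading is the baseline, later values are single readings, and the assumed SD and offset apply. The precision gain does not need the offset: averaging over 7 days at both ends cuts the standard error by about half or more at SD 10 with no week-to-week variation, and by about 40% to 50% with a week-to-week SD of 4 mmHg. Recruitment, retention and adherence are unaffected.

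**What to change.** In sections II.C and II.F:

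1. State that the Session 1 demonstration reading is not an outcome value.
2. In Session 1, train participants to take readings at a consistent time of day and under consistent conditions: seated after rest for the cuff, similar clothing for the scale.
3. Define each time point as the mean over a fixed window, for example 7 days, with a stated minimum number of readings. Use the same window length at baseline as at weeks 4, 8 and 12.
4. Schedule the Session 2 goal-setting after the baseline window closes. The plan gives no gap between Sessions 1 and 2, so without this the baseline could rest on very few days.

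The cost is protocol wording, a line in the training, a possible short wait before Session 2, and an averaging step on data already being collected.

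The plan should also state the limits. Baseline days would follow app set-up and possibly the My Plate review, so baseline would not be fully pre-intervention. A novelty effect lasting through the first week would remain, and averaging could make it easier to mistake for a result. Averaging does not replace a control group, so change in these measures should be reported as descriptive.

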The procedures should include the following:

A. Research Design

A feasibility study will be utilized to establish the recruitment, retention, and adherence with post-kidney transplant recipients using a consumer-based mHealth dietary app + health coaching.

B. Sample

Inclusion Criteria

(a) age 18 or older men and women, (b) functioning KTR (not on dialysis), (c) ability to speak, read, and hear English, (d) possession of a smartphone capable of accessing and downloading a mHealth dietary app (e) Wi-Fi or Internet access, (f) greater than 3 months post-transplant (due to medication adjustments and decreased functional levels), (g) not hospitalized, and (h) capable of self-consent per capacity screening.³²

Exclusion Criteria

(a) Participation in a weight loss program, (b) participation in a structured exercise program, and (c) diagnosis of dementia.

How will subjects be selected?

The participants will be recruited or contacted from a list of kidney recipients that have already requested they be contacted for future studies from our previous study (**IRB Protocol Number: 2017B0084**). This list consists of approximately 60 people. This study will also be advertised at the Ohio State University Medical Center Kidney Transplant monthly support group. Fliers with study information will be made available at the support group. The support group leader will also inform the group participants about the study.

After participants meet the initial screening requirements in the recruitment process, we will determine capacity to obtain verbal consent using the Evaluation to Sign Consent Form (ESC). The ESC consists of five questions (“What are risks associated with the study?” “What are two potential risks for participating in the study?” “What is expected from you in this study?” “What if you do not want to continue the study?” “What if you experience discomfort?”) and takes less than 10 minutes to complete. The ESC allows the participant to reflect upon their understanding of the research protocol by answering the five questions. Participants must answer all five questions correctly to be included in the study. Anybody who is able to answer all five questions correctly will then be read verbal consent script by the study team.

C. Measurement / Instrumentation

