Week 1-12 (Sessions 2-13) Time for session: 30 minutes	
Phase 1: The participant will place the goals (dietary and physical activity) into their “Lose-It” app via smartphone for goal attainment.
 
Phase 2: The participant and the RA will review the electronic report generated from the “Lose-It” app for monitoring or assessing progress for dietary intake and physical activity each week from baseline to week 12.
 
Phase 3: The RA will review with the participant each week for 12 weeks how many days they implemented and achieved the solution for their daily goals.
 
Phase 4: Time will be allowed for any questions.

Risk and Benefits

The risks for harm to you for participating in this study are minimal. You may feel uncomfortable about having the research team knowing about your dietary intake or physical activity level. It is not unusual for people with a transplant to occasionally have difficulty with being physically active and controlling their weight. We are trying to help people with these common problems.

If you agree to take part in this study, there may or may not be direct medical benefits to you.

We hope the information learned from this study will in the future benefit other patients with a kidney transplant who are having difficulty becoming physically active and assessing their dietary intake.

E. Internal Validity

In the previous K award²² study, we found that the primary reason for participants not enrolling (65%) into the study was due to the distance of traveling to the research site. Thus, there is a need to deliver the intervention activities in home settings via Zoom. The delivery of our study research activities is timely due to the Coronavirus (COVID-19) and the fact that our population is immunocompromised. Due to the recent pandemic outbreak of the coronavirus (COVID-19) and since our population is immunocompromised. We will promote sustainability for participating in the study by sending weekly text messages to the participants to thank them for their participation in the study. The conduct of this feasibility study will help identify other limitations to consider for future studies in a larger multisite clinical trial. We will collect data regarding the time spent on delivering the intervention so that we can conduct a cost-effective analysis at a later date.

F. Data Analysis

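### No weekly call, measure or analysis asks about or counts falls, hospital visits or graft problems during 12 weeks of activity coaching; a short fixed question would close the gap cheaply

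*Combined protocol and SAP*

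**What the plan says.** **Intervention.** I. Objectives plans 20 recipients in a single group for 12 weeks and hypothesises, among other changes, more minutes of physical activity per day. Under II.D, participants enter diet and activity goals in the app. Sessions 2-13 are 30-minute weekly video calls in four phases: entering goals, reviewing the app report, counting days achieved ("The RA will review with the participant each week for 12 weeks how many days they implemented and achieved the solution"), and time for questions.

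**Entry safeguards.** II.B requires "b) functioning KTR (not on dialysis" and "f) greater than 3 months post-transplant (due to medication adjustments and decreased functional levels), (g) not hospitalized". The consent-capacity check includes the item "What if you experience discomfort".

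**Measures.** Under II.C, comorbidity data "will be gathered using the Charlson Comorbidity Index", and frailty is scored. Weight, blood pressure and heart rate are recorded daily and synced; II.D says the research team has access to that database. Retention is recorded in REDCap as percent dropped.

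**Risk statement.** Risk and Benefits says "The risks for harm to you for participating in this study are minimal" and names discomfort about the team knowing one's diet or activity level.

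**Analysis.** II.F covers sample characteristics, the two aims, frailty at baseline and 12 weeks, and missing data: "We will carefully record and code various reasons for missing data".

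**The concern.** The intervention encourages people with a transplanted kidney to be more active. The questions a colleague planning the next trial would ask are simple: did anyone fall or get hurt, go to hospital unexpectedly, or have trouble with the graft? The plan has weekly contact in which to ask, but no stated question, form or summary for it.

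The consequence is one of collection and reporting. Events not asked about during the 12 weeks cannot be recovered reliably afterwards. If the final report mentions no harms, the reader cannot tell whether none happened or none came up. II.E says the study should help identify limitations to consider before a larger multisite trial, and a plain count of these events belongs with that. No estimate, test or sample size in the plan is affected.

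**Working it through.** The plan gives no event rate, safety figure or derivation of its sample size, so there is no figure to reproduce. The check is a reading of the text, followed by arithmetic for scale.

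**1. Where could an event be captured?**

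| Place | What it captures | Prompts for or counts events? |
|---|---|---|
| II.B entry criteria | Dialysis and hospital status at eligibility | No; no recheck is stated |
| II.B consent check | Understanding of what to do about discomfort, before enrolment | No |
| II.C daily weight, blood pressure, heart rate | Outcome data visible to the team | No; no threshold or action is stated |
| II.C and II.F frailty | A score at baseline and 12 weeks | No |
| II.D Phases 1-3 | Goals, app report, days achieved | No |
| II.D Phase 4 | Whatever the participant raises | Not prompted |
| II.F missing-data coding | Reasons when data are missing | Only if the event interrupts data |
| II.F analyses | Aims 1 and 2, frailty, missing data | No event summary |

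The case that escapes every row is a participant who has an event, does not raise it, and keeps logging.

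**2. How likely is there to be anything to record?** Inputs: n = 20 (I. Objectives); the 12-week risk per person, p, is assumed, because the documents give none. With independent participants, P(at least one affected) = 1 - (1 - p)^20.

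- p = 1%: 1 - 0.99^20 = 0.182
- p = 2%: 1 - 0.98^20 = 0.332
- p = 5%: 1 - 0.95^20 = 0.642
- p = 10%: 1 - 0.90^20 = 0.878
- p = 15%: 1 - 0.85^20 = 0.961

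The chance equals 50% at p = 1 - 0.5^(1/20) = 0.0341. Below a risk of about 3.4%, the likelier outcome is that there is nothing to record.

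**3. What would a count show?** Exact (Clopper-Pearson) two-sided 95% limits for x out of 20 are the 0.025 quantile of Beta(x, 21 - x) and the 0.975 quantile of Beta(x + 1, 20 - x).

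- 0/20: 0 to 1 - 0.025^(1/20) = 0.168, so 0 to 16.8%
- 1/20: 0.0013 to 0.2487, so 0.1% to 24.9%
- 2/20: 0.0123 to 0.3170, so 1.2% to 31.7%

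These intervals are wide. They describe what was seen and little more, but they cannot be given at all unless someone asks.

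**The case against.** **The plan does watch participants after entry.** A reader might infer that nothing checks on risk once people are enrolled. The documents do not support that. Weight, blood pressure and heart rate arrive daily in a database open to the team, and an RA meets each participant every week. This stands, and it makes the point smaller. It does not remove it, because these are outcome data with no stated alert or event form.

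**Immune status.** A reader might also lean on "the fact that our population is immunocompromised" in II.E as a sign of special hazard. There the phrase supports remote delivery during COVID-19. It says nothing about activity coaching, and no weight is put on it here.

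**Dropout reasons.** It would be too strong to say that medical reasons for stopping go unrecorded. Someone who stops produces missing data, and II.F commits to coding the reasons; forgetting to log is only an example. What remains is that no medical category is named and the coding is not tied to percent dropped. That is a reporting detail.

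**Unseen consent text.** The verbal consent script is not in the supplied text and may tell participants to report problems. That limits how firmly one can describe event capture. An instruction of that kind still would not supply a planned event summary.

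**Limited value of the count.** With 20 people and no control group, hospital visits and graft problems would mix with background disease. The count would test the minimal-risk statement only weakly, the plan prescribes no exercise dose, and every risk used above is assumed. All of this stands, and it is why the recommendation is description only and low in priority.

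**Conclusion.** The point holds as a minor, cheap improvement. The supplied text contains no prompted question and no planned summary for falls or injuries, unplanned hospital or emergency visits, or new dialysis or graft problems. As a result, a report of no harms could not be distinguished from not asking.

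Its size depends on an event risk the documents do not give. Over the assumed range of 1% to 15%, the chance of at least one affected participant goes from about one in five to near certainty. The calculation also assumes independent participants who are all followed for 12 weeks.

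Two stronger conclusions might be drawn and should not be. The gap is not evidence that the intervention is unsafe or that the minimal-risk statement is wrong; the documents contain nothing on either. Nor would closing it establish safety, show causation or support a go/no-go decision: even 0/20 is compatible with a true risk of up to 16.8%.

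**What to change.** **Change.** In each existing weekly call (Sessions 2-13), and at a last contact with anyone who stops, the RA asks the same short set of questions: any fall or injury; any unplanned hospital or emergency visit; any new dialysis or graft problem. The RA records date and outcome in REDCap for investigator review. II.F adds one line: the number of participants out of 20 with each event, with an exact 95% confidence interval, as description only.

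**Minor note.** Include a medical category in the reason coding II.F already plans, and show it beside percent dropped. With 20 participants, each dropout moves that figure by 1/20 = 5 percentage points.

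**Cost (minutes assumed).**

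- Calls: 20 × 12 = 240 calls × 2 minutes = 480 minutes = 8 RA hours. Per participant this is 12 × 2 = 24 minutes, or 2/30 = 7% of each call. It is a maximum, since anyone who stops has fewer calls.
- Last contacts: 2 to 6 people × 10 minutes = 20 to 60 minutes.
- Investigator review: 1 to 6 records × 15 minutes = 15 to 90 minutes.
- Total: 480 + 20 + 15 = 515 minutes (8.6 hours) to 480 + 60 + 90 = 630 minutes (10.5 hours), plus setting up one form.

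No new visits or procedures are needed, and no test or sample size changes. The downside is slightly longer calls and a record of background events that cannot be attributed without a control group.

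### The Aim 1 signed-rank test does not fit the primary outcomes: recruitment has no pairs, retention only re-counts dropouts, and adherence has no defined baseline

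*Combined protocol and SAP*

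**What the plan says.** Section I names recruitment, retention and adherence as the primary outcomes of a single-arm feasibility study with N = 20.

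Section II.F (Data Analysis, Aim 1) treats all three in one sentence. The variables are "percent approached, percent dropped, and percent to adhere to logging daily dietary and physical activity". They are to be summarised by means and standard deviations and "analyzed as differences between the baseline and 3-month measurements using the Wilcoxon Signed-Ranked test". No other test, confidence interval or feasibility criterion is given for Aim 1.

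Other sections bear on this:

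- Section II.B gives two recruitment sources. One is a contact list: "This list consists of approximately 60 people". The other is a monthly support group of unstated size: "Fliers with study information will be made available at the support group".
- Section II.C has the research assistant record recruitment and retention, each as a percentage; the app records adherence day by day.
- Section II.D has the app demonstrated and set up at the baseline session, and then: "The participants will be trained to enter their dietary intake and physical activity daily for 12-weeks".
- The hypothesis in Section I is that the intervention "will improve adherence for recording diet and physical activity".
- Section I also states: "We will assess changes over time for the primary outcome and secondary outcomes from baseline to 4, 8, and 12 weeks". Section II.F uses only baseline and 3 months for the primary outcomes.

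**The concern.** A signed-rank test needs two values of the same quantity from each participant. Recruitment supplies none. Retention supplies a pair only if it is coded per person, and then the first member is the same for everyone by construction. Adherence is a genuine per-person quantity, but there is no logging before the baseline session and no run-in, so the first member of the pair does not exist until someone names a window. The plan nevertheless states a directional hypothesis about adherence, and this is its only test.

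The descriptive side has gaps too. A mean and standard deviation do not describe a single study-level percentage. Read literally, the percentage approached does not measure enrolment.

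Section II.E expects the study to help shape a larger multisite trial. Its planners need rates and their uncertainty. The planned p-values give neither, and an adherence baseline chosen after the data are seen could settle the direction of the result.

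**Working it through.** The plan states no power, alpha, sidedness or expected dropout, so there is no figure of its own to reproduce. Two-sided 0.05 and 95% intervals are assumed below.

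**Inputs from the documents.** N = 20 (Section I); contact list of about 60 (Section II.B); 12 weeks of daily logging, so 12 × 7 = 84 days (Section II.D).

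**Recruitment.** There is one percentage for the study, fixed before follow-up. With no within-person differences, the test cannot be computed.

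**Retention.** Code dropped = 0 for all 20 at baseline and 0 or 1 at 12 weeks. Zero differences are discarded. The d remaining differences are tied and share one sign, so the exact two-sided p = min(1, 2 × 0.5^d). In the tie-corrected normal approximation without continuity correction, the statistic reduces to z = √d.

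| Dropouts d | Exact p | Approximate p | Retention, exact (Clopper-Pearson) 95% CI |
|---|---|---|---|
| 2 | 0.50 | 0.157 | 18/20 = 90% (68.3 to 98.8) |
| 4 | 0.125 | 0.046 | 16/20 = 80% (56.3 to 94.3) |
| 6 | 0.031 | 0.014 | 14/20 = 70% (45.7 to 88.1) |

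Significance first appears at 6 dropouts with the exact test and at 4 with the approximation. Either way it says only that several people left. With no dropouts, or with completers only, there is nothing to test.

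**Adherence (assumed data).** Suppose all 20 log 25 of 28 days (89%) in weeks 1–4 and 17 of 28 (61%) in weeks 9–12.

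- Baseline coded 0%, because no app logging existed before the first session (the plan does not say this): 20 positive differences, p = 2 × 0.5^20 = 0.0000019, improvement.
- Baseline taken as weeks 1–4: 20 negative differences, p = 0.0000019, decline.

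**Adherence denominator (assumed data).** Suppose 4 of 20 leave at week 4 and everyone logs 80% of days while enrolled. The figure while enrolled is 80%. Over 84 days for all enrolled it is (16 × 0.80 + 4 × 0.80 × 28/84)/20 = 69.3%. The plan does not say which is meant.

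**What recruitment could report.** Assume that all 60 on the list are approached. If 10, 15 or 20 of them enrol, the rates with exact 95% CIs are 16.7% (8.3 to 28.5), 25.0% (14.7 to 37.9) and 33.3% (21.7 to 46.7). The split between the list and the support group is not given.

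**The case against.** The strongest objection concerns adherence. It is measured per person and every day, and a signed-rank test on paired percentages is a standard choice at N = 20. Only the reference window is missing, which is under-specification rather than a wrong test. This stands as far as it goes: the test can be kept once windows are named. As written, though, the plan names none, and the hypothesis rests on it.

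The adherence example is also constructed. Identical counts for all 20 people and a 0% baseline produce the extreme p-values. That is fair: the example shows that the choice of baseline can reverse the conclusion, not how large the effect would be in practice.

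The retention threshold depends on the version of the test (4 or 6 dropouts). True, and both are shown; under both, p depends on the dropout count alone.

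The recruitment figures depend on the denominator. If approaches stopped after 30 people with 20 enrolled, the rate would be 66.7% (47.2 to 82.7), not 33.3%. This stands, and is a reason to log approaches. Stopping at the 20th enrolment also departs from binomial sampling, but the effect on the interval is small (upper limit for 20/60 of 45.6% rather than 46.7%).

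Finally, the percentages can be reported anyway, anyone can compute an interval from 16/20, and the protocol describes no progression rule driven by p-values. This limits the severity. It does not make the planned test informative. The difference in time points may be no more than an ambiguity, since assessing at four times and testing two can coexist.

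**Conclusion.** The concern holds. The Aim 1 test cannot be computed for recruitment, is uninformative for retention and is undefined for adherence until a baseline window is named. No other section repairs this.

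The recruitment conclusion needs no numerical assumption. The retention figures assume per-person coding and a two-sided test. The adherence reversal rests on assumed data and shows sensitivity to the baseline, not an expected effect.

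The point should be fixed but does not block the study: the feasibility percentages remain obtainable from the data to be collected, provided the number approached is recorded.

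**What to change.** Delete the Aim 1 signed-rank test as written, and the mean and standard deviation for recruitment and retention. In their place:

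1. **Recruitment:** consented divided by approached, for the contact list of about 60, with an exact 95% CI. State how many were approached and whether approaches stopped once 20 had enrolled. Report support-group enrolment as a count unless the number approached there is logged.
2. **Retention:** completed week 12 divided by enrolled, with an exact 95% CI.
3. **Adherence:** each person's share of the 84 days logged, for all enrolled, with median, interquartile range and a 95% CI whose target (mean or median) and method are named. Give the share of days logged while enrolled alongside. Define a logged day: diet, activity or both.
4. **Change in adherence, if wanted:** a signed-rank test between predefined early and late windows (for example weeks 1–4 versus 9–12), with a rule for people who leave before the late window. Both windows fall under coaching, so the result describes persistence of logging and not an effect of the intervention.
5. **Hypothesis:** reword the claim that the intervention improves adherence, since no pre-intervention logging exists.
6. **Time points:** align Sections I and II.F for the primary outcomes.

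The cost is SAP wording and a simple log of people approached, if none is kept. Sample size and visits are unchanged. The intervals will be wide at N = 20, which is an honest statement of what the study can show.
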